## G. Sample Size Considerations

We plan the study to have 90% power at the overall 0.05 significance level to be able to detect a relative improvement of 40% or more in mean opioid consumption(i.e., ratio of geometric means of 0.60) between any of the 3 interventions, assessing separately for 0-24 hours (primary outcome #1) and 24-48 hours (primary outcome #2) postoperatively. Assuming a coefficient of variation (CV = SD/mean) for opioid consumption of 0.85 [since the outcome is expected to be log-normal], the required sample size to will be 67 per group or 201 total. After adjusting for the interim analyses the maximum sample size will be 79 per group or a total of 237. Alternatively, for example, a total (maximum) sample size of 722 would be required to detect a more modest 25% reduction in the mean.

Internal pilot assessment of variability. At the second interim analysis, we will conduct an internal pilot study to assess the observed variability in the primary outcome and the related coefficient of variation (CV). If the CV is larger than planned in the protocol, we will resize the study accordingly, keeping everything else the same. For example, if the observed CV is 1.0 (instead of 0.85), the new maximum sample size would be a total of 298 patients to detect the same 40% relative reduction in the outcomes. The internal pilot assessment will not affect the type I error of the study nor alter the effect size of interest.

Adaptive design option. At the 3rd interim analysis we may consider an adaptive design in which the study is repowered for a smaller but still clinically important treatment effect. Specifically, if the conditional power at the 3rd look is between 30% and 75%, the DSMB (or Executive Committee) we will consider resizing the study to have 90% power to detect a relative reduction as small as 20% (i.e., a ratio of geometric means of 0.80). 

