#### ***Criterion for success of each intervention in each period.***

0-24 hours: for each of bupivacaine and exparel, success will be concluded if found to be superior over placebo (i.e., less opioid consumption). As well, exparel or bupivacaine will be concluded better than the other if found superior on opioid consumption.

24-48 hours: exparel will be concluded successful if found better than both placebo and bupivacaine in the 24-48 hours opioid consumption.

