## **F. Data Analysis**

Randomized groups will be compared for baseline balance using standard descriptive statistics and the standardized difference (difference in means or proportions divided by the pooled standard deviation).

**Primary Outcomes.** *Opioid consumption.* The following tests for superiority on opioid consumption will be conducted (see type I error control below): 1) 0-24 hours post-surgery: compare each of exparel and plain bupivacaine to placebo; and 2) 24-48 hours post-surgery: compare exparel to each of plain bupivacaine and placebo. Groups will be compared using linear regression on log-transformed morphine equivalents, with results reported as ratio of geometric means between each pair of interventions.

**Type I error control across Primary outcomes 1 and 2.** We will use a parallel gatekeeping procedure to control the type I error at 5% across the 2 primary outcomes. The 2 comparisons for the 0-24 hour period will constitute Set #1, and the 2 comparisons for the 24-48 hour period will constitute Set #2. Within each set we will use the Holm-Bonferroni (HB) multiple comparison procedure among the two comparisons. If either test in the first Set is significant (HB: significance criterion of 0.025 for smaller P-value and 0.05 for the larger), analysis will continue to Set #2. Otherwise, Set #2 will not be analyzed. If analysis proceeds to Set #2, the overall alpha for Set #2 will be  $0.05 \times$  proportion of significant tests in Set #1 (i.e., Set #2 alpha = either  $0.05 \times 1$  or  $0.05 \times .5 = 0.025$ ).

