**Figure 1.** Group sequential stopping boundaries as a function of sample size. Pink region represents futility. Lower blue represents efficacy of NAC, upper blue represents harm. Y-axis represents the treatment effect (Z= difference in means divided by standard error).

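### The success criteria, the gatekeeping plan and the sample size describe different families of primary tests, and the 0-24 h exparel-bupivacaine claim has no alpha

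*Combined protocol and SAP*

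**What the plan says.** Four places in the combined protocol and SAP define the primary comparisons.

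- **Section 3.G, Sample Size Considerations.** The target is "90% power at the overall 0.05 significance level" for a "ratio of geometric means of 0.60", "between any of the 3 interventions, assessing separately for 0-24 hours" and 24-48 hours. The result is given as "the required sample size to will be 67 per group or 201 total", or 79 per group (237 in total) after allowing for interim looks. Two further maximum totals are given: 722 for a 25% reduction, and 298 if the CV is 1.0. No per-comparison alpha is given.
- **Section 3.F, Type I error control.** Set #1 (0-24 h) compares exparel and bupivacaine each with placebo. Set #2 (24-48 h) compares exparel with bupivacaine and with placebo. Holm applies within each set, with a "significance criterion of 0.025 for smaller P-value and 0.05 for the larger". Set #2 receives 0.05 if both Set #1 tests succeed and 0.025 if one does.
- **Section 2, criterion for success of each intervention.** At 0-24 h, "exparel or bupivacaine will be concluded better than the other if found superior on opioid consumption".
- **Section 2, success criteria under Primary Aim 2.** Noninferiority between bupivacaine and exparel at 0-24 h is part of success. No margin is given.

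**The concern.** These sections do not describe one family of tests. Six comparisons are sized and four are tested. The success criteria add exparel versus bupivacaine at 0-24 h, as superiority in one place and noninferiority in another. That pair is in neither set and has no alpha. Conversely, bupivacaine versus placebo at 24-48 h is sized but never tested.

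Two things are at stake. First, section 3.F promises 5% error control across the two primary outcomes, and a primary-window conclusion drawn outside the two sets breaks that promise. It concerns the head-to-head question that motivates the trial. Second, the 90% in section 3.G is not the power of the tests in section 3.F. The unstated alpha also carries forward, because the resizing at the second interim keeps everything but the CV fixed.

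**Working it through.** **Inputs.** From section 3.G: power 90%; ratio 0.60, so δ = |ln 0.60| = 0.5108; "Assuming a coefficient of variation (CV = SD/mean) for opioid consumption of 0.85", so log-scale SD σ = √ln(1 + 0.85²) = √0.5438 = 0.7374; equal arms. Sidedness is not stated. I assume two-sided, because the boundary figure's legend reads "Lower blue represents efficacy of NAC, upper blue represents harm".

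**1. Reproducing the 67.** Normal approximation: n per group = 2(z₁₋α/₂ + z₀.₉₀)²σ²/δ². At α = 0.05/6 this is 2 × 3.920² × 0.5438 / 0.2609 = 64.04, so 65. The exact noncentral-t calculation gives 66. For α = 0.05/k:

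| k | exact-t n per group | 25% reduction, total × 79/67 | CV 1.0, total × 79/67 |
|---|---|---|---|
| 1 | 45 | 495 | 202 |
| 2 | 54 | 584 | 241 |
| 3 | 58 | 633 | 262 |
| 4 | 62 | 672 | 276 |
| 5 | 64 | 700 | 287 |
| 6 | 66 | 722 | 297 |
| 7 | 68 | 743 | 304 |
| Plan | 67 | 722 | 298 |

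The k = 6 entries are 204 × 3 × 79/67 = 721.6 and 84 × 3 × 79/67 = 297.1. The 67 alone would allow k = 6 or 7. The 722 and 298 point to k = 6, which is also the number of comparisons that section 3.G describes (3 pairs × 2 windows).

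**2. Fixed-design power of the tests in section 3.F, 67 per group.** The noncentrality is 0.5108 / (0.7374 × √(2/67)) = 4.01. Exact-t power per comparison is 90.6% at 0.05/6, 92.8% at 0.0125, 95.8% at 0.025 and 97.8% at 0.05.

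Simulating the full gatekeeping procedure (no interim looks, within-patient correlation 0 to 0.8) gives:

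- both actives work at 0-24 h and exparel works at 24-48 h: about 93% for all four tests;
- only exparel works at 0-24 h, so Set #2 usually receives half the alpha: about 90-92% for both Set #2 tests.

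**3. Power with the interim looks, 79 per group.** I used four equally spaced looks, alpha spending with gamma -4, and futility spending of 0.025 per look as in the Interim Analyses text. These were applied to the 40% reduction of section 3.G, with the futility stops obeyed. Power per comparison is 90.9% at 0.05/6, 91.5% at 0.0125 and 92.2% at 0.025. By the third look the futility rule has already spent 7.5% of power whatever the alpha, so the gain from a looser alpha is small.

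**4. Cost of the extra claim.** Under the global null, Set #2 is reached only after a false rejection in Set #1. The family-wise error of the section 3.F procedure is therefore the chance of any Set #1 rejection. One million simulated trials (normal approximation, no interim looks) give 4.6%. Adding a two-sided exparel-bupivacaine test at 0-24 h at an assumed 0.05 gives 8.5%. Both figures are stable for correlations of 0, 0.5 and 0.8.

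**The case against.** The strongest defence is that sizing at a Bonferroni level stricter than the Holm levels actually used is a safe choice: 90% then holds as a lower bound for each planned test. That stands. The alpha basis is also an inference, and exact t gives 66 rather than 67. That stands too, although three figures agree with it.

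Three stronger readings are tempting, and the documents do not support them.

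- *The trial enrols more than it needs.* At 0.025 a single comparison needs 54 per group. That scales to 54 × 79/67 = 64 rather than 79, or 45 fewer patients in total. But section 2 requires exparel to beat both placebo and bupivacaine at 24-48 h. With 54 per group and no looks, power is about 82-84% for all four tests. It is 77-81% for both Set #2 tests if only exparel works at 0-24 h. On that path it is the 67 that delivers about 90%.
- *The planned tests have 96% power.* That is a fixed-design figure at 0.025. With the stated futility rule followed it is about 92%.
- *The trial is underpowered because its test families disagree.* The mismatch runs the other way for the four gated tests.

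It can also be said that the unallocated comparison is a multiplicity gap rather than an arithmetic error. That is correct, and it is the weightier part of the point.

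**Conclusion.** The inconsistency is real and should be corrected. Its main consequence is for error control: acting on the success criteria as written allows a primary-window conclusion outside the 5% scheme. The false-claim rate then rises from about 4.6% to about 8.5% under the global null if that test is run two-sided at 0.05. The plan gives no level, so the 0.05 is my assumption. The noninferiority version cannot be evaluated at all without a margin.

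The sample size part is a matter of stating the right figures. Section 3.G appears to rest on six tests at a two-sided 0.05/6, while section 3.F runs four tests at 0.0125 to 0.05. Power for those four is at or somewhat above the stated 90%, by an amount that depends on the gating path and on whether futility stops are followed. Nothing here supports a change in enrolment.

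**What to change.** 1. **Success criteria (section 2).** Remove the 0-24 h exparel-bupivacaine superiority and noninferiority conclusions, or label both exploratory. Both places need the edit, since changing one leaves the other. Alternatively, place the comparison in the gatekeeping scheme with its own alpha, and with a margin if noninferiority is kept. In that case recompute the Set #1 Holm levels, the share of alpha passed to Set #2, and the power.
2. **Section 3.G.** State the per-comparison alpha and sidedness behind the 67, 722 and 298, and restate power for the section 3.F tests. If the four tests are kept, suitable fixed-design figures at 67 per group are 95.8% per comparison at 0.025, 92.8% at 0.0125, about 93% for all four, and about 90-92% for both Set #2 tests if only exparel works at 0-24 h. For 79 per group with four looks and futility followed, give about 92% at 0.025 and 91.5% at 0.0125, and say that power is higher only if futility stops are not followed.
3. **Resizing.** Say which alpha the second-interim resizing will use.

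The cost is wording and restated figures, with no change in enrolment. Only the alternative in item 1 needs new calculations.
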